13.6 Termination of Study Site Participation

The sponsor reserves the right to stop study enrollment at a study center at any time during the study. Specific instances that may precipitate terminating a study center may include the following:

- Unsatisfactory participant enrollment
- Failure to comply with protocol
- Failure to obtain informed consent
- Inaccurate and/or incomplete data recording on a recurrent basis

- Failure to report SAEs in timely manner on a recurrent basis
- Loss of (or unaccounted for) investigational product inventory
- Severe protocol deviations without justification or failure to implement corrective actions

14 DATA HANDLING AND RECORD KEEPING

For the study duration, the investigator will maintain complete and accurate documentation including but not limited to the following: medical records, study progress records, laboratory reports, CGM data, case report forms, signed informed consent forms, device records, and correspondence with the IRB and study monitor/sponsor, AE reports, and information regarding participant discontinuation or study completion.

14.1 Source Documentation

For the duration of the study, the investigator shall take responsibility for maintaining complete and accurate source documentation.

The following materials should be included in the patient record:

- Participant medical history/physical condition prior to study involvement
- Dated and signed notes on the day of entry into the study referencing the study, the sponsor, participant study ID number, and a statement confirming informed consent
- Dated and signed notes from each participant's visit (for specific results of procedures and exams)
- AEs reported and their outcome including supporting documents
- Participant's condition upon study completion or withdrawal

14.2 Case Report Form Completion

Data will be collected primarily using the electronic case report forms (eCRF). Laboratory data and CGM data may be collected separately and integrated into the data analysis.

Primary data collection will be performed by site staff trained on the protocol and eCRF completion. All data fields will be completed where appropriate. However, if data are not available (i.e., missed visit, etc.), the site will receive instruction regarding electronic documentation. As data are entered, automated crosscheck programs will search for any data discrepancies in the eCRFs. Appropriate error messages will be generated, allowing for the modification and/or verification of the entered data. Queries will generally be sent to the investigational site using an electronic data query system that includes an automated audit trail of the corrections. The investigator, or designee, will certify that the data are complete and accurate by applying an electronic signature to the eCRF. Any subsequent alterations, corrections, or additions will be reviewed and electronically signed by the investigator prior to the database lock.

The sponsor or designee will provide clinical monitoring to include eCRF review and parity checks with the source documentation, including operator worksheets retained with eCRF documentation and health care facility charts.

14.3 Record Retention

The investigator/site will maintain all records pertaining to this study for the later of (a) ten years following study completion, or (b) ten years after the study has been terminated by the sponsor, or (c) as otherwise instructed by the sponsor. Investigator will be notified by sponsor of the date of completion or discontinuation of the study.

To comply with these requirements, the investigator will not dispose of or transfer any records relevant to this study without either (1) written permission from the sponsor, or (2) providing an opportunity for the sponsor to archive the records with an external vendor.

15 ETHICAL CONSIDERATIONS

15.1 Institutional Review Board

IRB approval for the protocol and informed consent form will be obtained by the investigator prior to study participation by participants. The approval letter must be obtained prior to beginning this study and a copy must be provided to the sponsor. No changes will be made to the protocol or informed consent form without appropriate approval from the IRB, the sponsor and/or the regulatory agencies. Additionally, the investigator or representative will provide an IRB membership list or assurance number to the sponsor or its designee.

As per oversight IRB requirements, the investigator will report study progress until it is completed. Further, any protocol amendments as well as associated informed consent changes will be submitted to the IRB and written approval must be obtained prior to implementation.

15.2 Informed Consent

Written informed consent must be obtained prior to any study-related activities and the index procedure.

The investigator should clearly explain that this is an elective procedure and should discuss the potential risks and benefits associated with participation in this study.

Participants providing informed consent agree to permit the sponsor or designee access to pertinent information in their medical records and other study related data concerning their participation in this study. This confidential patient information may be shared with regulatory agencies as required; however, the sponsor undertakes not to otherwise release the participant's personal and private health information.

15.3 Confidentiality

The identity of participants enrolled in the study and the information contained in their study records will be kept confidential by the sponsor. As part of the investigator training session, investigators will be instructed in the importance of confidentiality and the techniques for protecting participant's privacy and rights. Participant's personal information will be handled at all times in accordance with appropriate confidentiality standards and applicable data protection and local privacy laws.

Each participant will be assigned a study identification number to be used on eCRFs and other study records sent to the sponsor or its designee. Initials will also be used to track study participants.

Confidentiality will be protected as much as possible throughout the study. Medical records will be reviewed by representatives of the sponsor and/or its designee and will be made available for review as required by the IRB and FDA regulations. Results of data collected will be reported as statistical information only. The participant's name will not be used or otherwise disclosed unless required by law or regulation.

16 INVESTIGATIONAL DEVICE MANAGEMENT

16.1 Device Accountability

The sponsor will only distribute investigational devices to sites that are part of the clinical investigation. The sponsor will maintain complete, current and accurate records pertaining to the distribution of the investigational devices and follow record keeping requirements in accordance with Good Clinical Practices and FDA regulations.

The investigator is responsible for maintenance of adequate records of the receipt, disposition, and/or return of all investigational devices distributed to their site. At study termination, or termination of the site from

51

participation in the study the sponsor will provide specific instructions to the study sites on unused investigational devices.

Use of the investigational device outside of the protocol (e.g., compassionate use) without prior written approval is strictly forbidden and may constitute grounds for removal of the investigator/site from the study.

16.2 Device Return

All unused investigational devices, including those unused due to malfunction, device failure, device complaint or device dropped on the floor, must be returned to the sponsor or its designee immediately according to the returned goods process. All devices and/or remaining components that are associated with a device malfunction or clinical procedural failure should be returned to the sponsor.

APPENDIX 1. DEFINITIONS

Adverse Event Severity

- Mild: no or transient symptoms, no interference with the participant's daily activities
- Moderate: marked symptoms, moderate interference with the participant's daily activities.
- Severe: incapacitating with inability to perform daily activities; unacceptable.

The Los Angeles Classification of esophagitis¹⁴

- Grade A: One (or more) mucosal break no longer than 5 mm that does not extend between the tops of two mucosal folds
- Grade B: One (or more) mucosal break more than 5 mm long that does not extend between the tops of two mucosal folds
- Grade C: One (or more) mucosal break that is continuous between the tops of two or more mucosal folds but which involve less than 75% of the circumference
- Grade D: One (or more) mucosal break which involves at least 75% of the esophageal circumference

Hypoglycemia (ADA 2020)

- Level 1 hypoglycemia is a blood glucose concentration 54–70 mg/dL (3.0–3.9 mmol/L).
- Level 2 hypoglycemia is a blood glucose concentration <54 mg/dL (3.0 mmol/L), which is typically the threshold for neuroglycopenic symptoms.
- Level 3 hypoglycemia is a clinical event characterized by altered mental and/or physical functioning that requires assistance from another person for recovery

Severe hypoglycemia: Level 3 hypoglycemia per ADA 2020 definition.

Documented symptomatic hypoglycemia: An episode during which typical symptoms of hypoglycemia are accompanied by a measured plasma glucose concentration \leq 3.9 mmol/L (70 mg/dL).

Probable symptomatic hypoglycemia: An episode during which symptoms of hypoglycemia are not accompanied by a plasma glucose determination but that was presumably caused by a plasma glucose concentration $\leq 3.9 \, \text{mmol/L} (70 \, \text{mg/dL})$.

Severe hyperglycemia: for purpose of this study, severe hyperglycemia is defined as FPG > 270 mg/dL confirmed by repeated measures more than 3 days apart

Diabetic ketoacidosis (DKA): an acute, major, life-threatening complication of diabetes characterized by hyperglycemia, ketoacidosis, and ketonuria.

APPENDIX 2. SCHEDULE OF ACTIVITIES

	b o	П	Ire	_	2	4	æ	12	91	02	24	87	32	36	0#	4	48 tudy	e uafi 24	ire atio
	Screening	Baseline ^{III}	Index Procedure	Week 1	Week 2	Week 4	Week 8	Week 12	Week 16	Week 20	Week 24	Week 28	Week 32	Week 36	Week 40	Week 44	Week 48 End of Study	Premature discontinuati on within 24 weeks	Pre-mature discontinuatio n post 24
Clinic Visit(V)/Remote Visit (R)	R1	V2	V3	V/R4	R5	V/R6	R7	V/R8	R9	R10	V11	R12	R13	V/R14	R15	R16	V17	V17A	R17A
Timing of visit (weeks)	-12	-3	0	1	2	4	8	12	16	20	24	28	32	36	40	44	48		
Visit window (days)	-84 to -5	-21 to -1	-	±2	±3	±5	±7	±7	±7	±7	±7	±7	±7	±7	±7	±7	+30		
SUBJECT RELATED INFO/ASSESMENTS																			
Informed consent	X																		
In/exclusion criteria	X	X																	
Medical history/Diabetes history	X			2															
Concomitant medication	X	X	X	X		X		X			X			X			X	X	X
Demographics	X																		
Treating physician diabetes assessment and medication review		X	X	Х	X	X	X	X	X	X	X	X	X	X	X	Х	X	X	
Lifestyle Counseling		X		X	X	X	X	X	X	X	X	X	X	X	X	X	X	X	
Diabetes education, Handout and instruct in CGM use		X																	
Handout ID card		-	X	2		Al sc			3				8			2			
Study Exit																	X	X	X
VITAL SIGNS AND PHYSICAL EXAMINATION																			
Height		X		2					3				8			2		2	
Body weight		X		X		X		X			X			X			X	X	
BMI		X		X		X		X			X			X			X	X	
Waist circumference		X		2				X			X			X			X	X	
Blood pressure and pulse rate		X	X	X		X		X			X			X			X	X	
Physical examination		Х															X	X	
LABORATORY TESTINGS																			
Fasting plasma glucose	Х	Х				X		X ^[6]			X			X			X ^[6]	Х	
HbA1c	X	Х				X		X			X			X			X	X	
Fasting insulin		X				X		X ^[6]		\vdash	X			X			X ^[6]	X	
Fasting serum C-peptide	X			2		al co			3				8						

	Screening	Baseline ^[1]	Index	Week 1	Week 2	Week 4	Week 8	Week 12	Week 16	Week 20	Week 24	Week 28	Week 32	Week 36	Week 40	Week 44	Week 48 End of Study	Premature discontinuati on within 24 weeks	Pre-mature discontinuatio n post 24
Clinic Visit(V)/Remote Visit (R)	R1	V2	V3	V/R4	R5	V/R6	R7	V/R8	R9	R10	V11	R12	R13	V/R14	R15	R16	V17	V17A	R17A
Timing of visit (weeks)	-12	-3	0	1	2	4	8	12	16	20	24	28	32	36	40	44	48		
Visit window (days)	-84 to -5	-21 to -1	-	±2	±3	±5	±7	±7	±7	±7	±7	±7	±7	±7	±7	±7	+30	37	
MMTT (Mixed meal tolerance test)		X	_	5				X	3								X	X	
HOMA-IR		X				X		X			X			X			X	X	
Fasting lipid panel		X		2							X						X	X	
Metabolic Panel [2]	X	X		X				X			X			X			X	X	
Pancreatic Enzyme (Lipase, Amylase)		X		X				X											
Serum Iron, ferritin, transferrin, saturation, serum folate, Vitamin D, Vitamin B12		Х									Х						X	Х	
CBC with differential	X	X		X		X		X			X			X			X	X	
Serum Glutamic acid decarboxylase antibody (Anti-GAD)	X																		
Thyroid-stimulating hormone (TSH)	X							$X^{[3]}$			$X^{[3]}$			$X^{[3]}$			$X^{[3]}$		
H. Pylori test	X	X																	
Pregnancy test [4]	X	X																	
International Normalized Ratio (INR) [7)		X																	
EKG		X																	
ENDOSCOPIES																			
DMR procedure			X																
Endoscopic follow up						X					X ^[5]								
SAFETY																			
Hypoglycaemic episodes	X	X	X	X	X	X	X	X	X	X	X	X	X	X	X	X	X	X	X
CGM		X	X	X	X	X	X	X	X	X	X	X	X	X	X	X	Х	X	X
Adverse events	X	X	X	X	X	X	X	X	X	X	X	X	X	X	X	X	X	X	X

^[1] Screening and baseline visits may be combined if screening visits or tests falls within baseline visit window.

^[2] Metabolic panel includes albumin, total protein, ALP, ALT, AST, bilirubin, BUN, creatinine, BUN/creatinine ratio, eGFR.

^[3] For participants on oral thyroid replacement therapy only.

^[4] For women with child-bearing potential.

^[5] Required if there were positive findings in the treated area at the 4-week endoscopy.

^[6] Only when MMTT is not performed.

^[7] INR is required prior to procedure only if participant is on Warfarin.

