7.9 Mixed Meal Tolerance Test

Following a minimum of 8-hour fast, the participant will undergo an MMTT which involves the consumption of a standardized mixed meal, consisting of 200ml of Ensure Plus and an Optifast bar with a combined calorie of 533 Cal (carbohydrate 63.4g, protein 31.8g, fat 17.4g, Fiber 6.7g), and collection of timed serial blood samples for measurement of plasma glucose, insulin and C-peptide through 180 minutes after consumption of the standardized meal (with no additional food intake during this time).

Participants will wear a CGM during the test. Prior to the test, the fasting glucose level between 70 mg/dL and 200 mg/dL will be confirmed via CGM reading or a capillary blood glucose measurement. The MMTT will only be performed if fasting glucose is within the range. If the fasting glucose is outside of this range, the test may be rescheduled once within the time window for this visit.

The participant should not take his/her glucose-lowering medications in the morning but instead bring the medications to the test. The medications should be taken after the test.

The MMTT should be performed in a laboratory with adequate emergency supplies in the event of severe hypoglycemia or severe hyperglycemia. The test should be started between 7AM and 11AM. A cannula is placed in a forearm vein. The standardized meal will be consumed within 5 minutes, and the blood samples will be collected within 15 minutes before consuming the standardized meal (ie, "0 minutes"), and at 10, 20, 30, 60, 90, 120, and 180 minutes after consumption. Blood sampling should occur as close as possible to the specified times (\pm 5 minutes) for the MMTT. After the test is completed, the participant may eat food and take his/her medications as prescribed by the investigator. Stable and acceptable glucose levels (glucose between 70-270 mg/dL over a 15 minutes) should be confirmed via CGM reading or a capillary blood glucose measurement prior to participant's discharge. For participants with glucose levels \leq 100 mg/dL, the glucose level should not be trending down in the 15-minute observation period and if it is, it should be treated until the glucose level is rising prior to discharge.

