The MMTT will be performed at the time points specified in the SoA (Appendix 2). The test requires the participant to visit to the testing laboratory. If the risk of potential COVID-19 exposure overweighs the benefit of performing the test in the opinion of the Investigator, the investigator may decide not to perform this test but perform tests for HbA1c, FPG and insulin instead. Follow-up MMTT will only be scheduled in participants who had baseline MMTT data.

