This visit will be performed onsite. The following evaluations/procedures are to be performed. Participant's study eligibility will be reconfirmed at this visit.

- Physical examination
- Anthropometric measurements including height, weight and waist circumference
- Vital signs
- Adverse event (changes in medical history)
- Concomitant medications
- 12-lead EKG
- Laboratory tests:
 - o Hematology (CBC with differentials)
 - Metabolic panel
 - o Glycemic parameters (HbA1C, MMTT, HOMA-IR)
 - Fasting lipid panel
 - o Lipase, Amylase
 - o Serum iron, ferritin, transferrin, saturation, serum folate, Vitamin D, Vitamin B12
 - o International normalized ratio (INR) for participants on Warfarin (may be performed on Day 0)
- H. Pylori breath or stool test
- Pregnancy test for females capable of becoming pregnant
- Assessment for eligibility
- Preparation with gastroenterologist for procedure, medication management per Section 6.
- Diabetes education, including instruction on CGM use
- Treating physician review of diabetes history and titration of glucose-lowing medications per Section 6.2
- Review CGM data
- Lifestyle counselling

If the participant is no longer eligible for the study due to a change in the participant's condition, such as pregnancy, abnormal blood test values, HbA1C outside of the protocol range, or weight change resulting in a BMI outside of the protocol range, the participant will be excluded from the study and documented as a screen failure.

The screening and baseline visit may be combined if the screening visit falls within the baseline visit window. In this case, data collected during the combined visit will serve as both screen and baseline data.

It is recognized that new COVID-19 restrictions may cause delays in scheduling the index procedure, resulting in the baseline visit out of window. In case the baseline visit is out of visit window, investigator will reassess participant's eligibility by evaluating any changes in participant's medical history and medications, Investigator's assessment will be documented on eCRF. The following tests will be repeated for safety considerations or to serve as baseline data:

- Laboratory tests:
 - Hematology (CBC with differentials)
 - o Glycemic parameters (FPG, HbA1C, insulin, HOMA-IR)
- Pregnancy test for females capable of becoming pregnant (may be performed on Day 0)
- Anthropometric measurements including weight and waist circumference (may be collected on Day
 0)

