### **8.6.** Unscheduled Visit Information

Information for this presentation of the recorded data will come from the individual datasets where the visit name is listed as *Unscheduled*. Listing 16.4.9 entitled *Unscheduled Visit Information* will be sorted by site number, and patient.

The table below provides the specification for assignment of an unscheduled visit. If there are multiple records within an interval, date of the latest record will be used.

			Protocol Visit Window			Expanded Visit Window		
Visit Name	Clinic (Visit) / (R)emote Visit	Timing of the Visit (weeks)	Protocol Visit Window (days)	First Interval Day	Last Interval Day	First Interval Day	Last Interval Day	Expanded Visit Window (days)
Screening	R1	-12	-84 to -5	-84	-5			
Baseline[1]	V2	-3	-28 to -1	-28	-1			
Index Procedure	V3	0						
Week 1	R4	1	±2	5	9	5	9	2
Week 2	R5	2	±3	11	17	10	18	4
Week 4	V6	4	±5	23	33	19	37	9
Week 8	R7	8	±7	49	63	38	74	18
Week 12	R8	12	±7	77	91	73	95	11
Week 16	R9	16	±7	105	119	96	128	16
Week 20	R10	20	±7	133	147	129	151	11
Week 24	V11	24	±7	161	175	152	184	16
Week 28	R12	28	±7	189	203	185	207	11
Week 32	R13	32	±7	217	231	208	240	16
Week 36	V14	36	±7	245	259	241	263	11
Week 40	R15	40	±17	273	287	264	296	16
Week 44	R16	44	±7	301	315	295	321	13
Week 48 (End of Study )	V17	48	30	306	366	322	366	14

Visit Name	Clinic (Visit) / (R)emote Visit	Timing of the Visit (weeks)	Target Visit Day	Number of Days on Either Side of the Target Day to define the Expanded Time Window
Screening	R1	-12		
Baseline[1]	V2	-3		
Index Procedure	V3	0		
Week 1	R4	1	7	2
Week 2	R5	2	14	4
Week 4	V6	4	28	9
Week 8	R7	8	56	18
Week 12	R8	12	84	11
Week 16	R9	16	112	16
Week 20	R10	20	140	11
Week 24	V11	24	168	16
Week 28	R12	28	196	11
Week 32	R13	32	224	16
Week 36	V14	36	252	11
Week 40	R15	40	280	16
Week 44	R16	44	308	13
Week 48 (End of Study )	V17	48	336	14

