### **Fourth Secondary Endpoint**

The distribution of this endpoint is continuous. The primary population for analysis of this endpoint will be the FAS population.

Change from baseline (post-baseline minus baseline) in Fasting plasma glucose (FPG) reported for each pre-specified study visit.

The pre-specified study visits where FPG is recorded is Week 4, 12, 24, 36, 48.

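### FPG and HOMA-IR come from a glucose-gated, re-bookable meal-test sample at Weeks 12 and 48 but from a plain fasting draw at Weeks 4, 24 and 36, and the baseline source is not named

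*Protocol*

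**What the plan says.** **Follow-up schedule (Protocol Appendix 2).** FPG and fasting insulin carry an unconditional mark at baseline and at Weeks 4, 24 and 36. At Weeks 12 and 48 both carry footnote 6: "Only when MMTT is not performed". HOMA-IR is marked at all of these visits. The MMTT is marked at baseline, at Weeks 12 and 48, and at the early-discontinuation visit.

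**The gate (Protocol 7.9).** Before the test, "the fasting glucose level between 70 mg/dL and 200 mg/dL will be confirmed via CGM reading or a capillary blood glucose measurement". Then: "If the fasting glucose is outside of this range, the test may be rescheduled once within the time window for this visit". The same section adds that "Follow-up MMTT will only be scheduled in participants who had baseline MMTT data". Where COVID-19 exposure is the concern, "the investigator may decide not to perform this test but perform tests for HbA1c, FPG and insulin instead".

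**Baseline.** The baseline visit text (Protocol 7.13.2) lists "Glycemic parameters (HbA1C, MMTT, HOMA-IR"), with no separate FPG, whereas Appendix 2 marks FPG and insulin there as well as the MMTT. If the baseline visit falls out of window, the tests to be repeated include FPG, HbA1c, insulin and HOMA-IR but no MMTT. SAP Section 7 defines baseline as the value recorded immediately before the procedure and does not name the sample.

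**Analysis.** For FPG, SAP Section 9 states: "The pre-specified study visits where FPG is recorded is Week 4, 12, 24, 36, 48". HOMA-IR has the same visits. SAP Section 4.2.1 puts each endpoint in a repeated-measures model with Week 24 as the principal time point.

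**The concern.** One endpoint in one longitudinal model is collected under two sampling rules, and one of those rules depends on the glucose level itself. At Weeks 12 and 48 a participant whose first reading is in range keeps that day's sample. A participant out of range may be brought back on another day, and the second sample can become the visit value. Replacing extreme first readings and leaving the rest alone shifts the visit mean even when nothing has changed in the patient.

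At stake are the Week 12 and Week 48 changes in FPG and HOMA-IR and the shape of the by-visit trajectory. A step between the gated visits (12, 48) and the plain-draw visits (4, 24, 36) could be read as a treatment pattern. If the baseline value is itself a gated sample, every change score inherits the shift, including the principal one at Week 24. The SAP neither names the source sample nor flags re-booked tests.

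**Working it through.** The plan states no figure on this point, and its sample size of 20 has no calculation behind it, so there is nothing to reproduce. The size was explored by simulation, with 1,000,000 participants per scenario.

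**From the documents:** gate 70-200 mg/dL, one re-booking, gate read on CGM or capillary meter, follow-up MMTT only after a baseline MMTT.

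**Assumed:** mean FPG 160, 180 or 200 mg/dL; between-person SD 30 or 40; day-to-day SD (sw) 12, 20 or 28; gate reading error SD 10; personal means held within 100-270; true change 0 or -25; every out-of-range test re-booked.

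**Model.** With personal mean m, plasma on attempt k is Pk = m + N(0, sw), and the gate reading is Gk = Pk + N(0, 10). The recorded value is P1 if 70 ≤ G1 ≤ 200, otherwise P2. P2 is either the re-booked pre-meal sample or, if the second attempt also fails, the plain draw that footnote 6 restores. Participants without a baseline MMTT get a plain draw at follow-up. Bias = mean estimated change minus true change; negative is toward benefit.

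**Who is re-drawn.** With no true change, 0-2.3% of first follow-up readings are below 70 and 12-50% are above 200. The shares actually re-tested are 7-25%, because participants who never passed the baseline gate have no follow-up MMTT.

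**Bias in the Week 12 or 48 change (mg/dL):**

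| Baseline FPG source | True change 0 | True change -25 |
|---|---|---|
| A: plain draw | -0.6 to -5.1 | -3.0 to +0.9 |
| B: gated MMTT sample | +0.1 to +2.3 | +1.0 to +4.5 |

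In the middle scenario (mean 180, sw 20, no true change), A gives -2.8 and -2.2 for between-person SD 30 and 40, and B gives +0.8 for both.

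**Week 24 under B.** Follow-up is a plain draw, so only the baseline shift remains, and it equals B minus A. With no true change, the smallest value is 0.14 - (-0.68) = +0.8 (mean 160, SDs 30 and 12). The largest is 2.26 - (-5.05) = +7.3 (mean 200, SDs 30 and 28). Simulating it directly gives the same range. Under A, Week 24 has no gate at either end.

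**Scale.** At sw = 20 the standard error of a mean change is 20 × √(2/10) = 8.9 mg/dL for n = 10 and 20 × √(2/20) = 6.3 for n = 20.

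**HOMA-IR.** The documents give no formula. With glucose × insulin / 405 and insulin 15 (both assumed), a 3 mg/dL shift is 3 × 15 / 405 = 0.11 units. This ignores any change in insulin between attempts.

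**Under the remedy.** With the first fasting sample at both ends, no value is replaced because of its size, so the re-test bias is 0 by construction.

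**The case against.** A reader might infer that only high readings get a second chance and that the change from baseline is therefore biased toward benefit. The documents do not support that. The gate is two-sided. Its action mainly on high readings is a consequence of the assumed FPG levels, not of the text. The direction also depends on the baseline sample. A baseline MMTT passes through the same gate, and if its pre-meal sample supplies baseline FPG, the bias runs against benefit in every scenario examined.

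Other points on that side also stand:

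- Re-booking is optional, so applying it to every out-of-range test gives an upper-end picture.
- The gate is a CGM or capillary reading, not the laboratory FPG.
- Participants without a baseline MMTT never meet the follow-up gate.
- Week 24, the principal time point, has no follow-up gate.
- The SAP calls its testing informative only, and these are two of 18 secondary endpoints in a 20-patient feasibility study.
- The rule in SAP 8.6, "If there are multiple records within an interval, date of the latest record will be used", is introduced for assigning unscheduled visits. Applying it to a test re-booked inside a scheduled window is an inference.

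It can also be said that a failed first attempt is an occasion when the MMTT was not performed, so footnote 6 may already require a plain draw that day. On that reading two fasting values exist for one visit, and nothing clearly says which is analysed. The gap moves; it does not close.

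**Conclusion.** The point holds in this form: FPG and HOMA-IR are sampled under a value-dependent rule at Weeks 12 and 48 and under a plain rule at Weeks 4, 24 and 36, and the baseline source is unspecified. No passage corrects this. That the pre-meal sample supplies FPG at Weeks 12 and 48 follows from footnote 6 together with the visits the SAP analyses; no passage says so outright.

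The likely effect is a few mg/dL, smaller than the standard error at these sample sizes, but systematic. Its direction cannot be settled. Appendix 2 leans toward a plain baseline draw, the in-window baseline text leans toward the MMTT sample, and out-of-window repeats have no MMTT, so the source may even differ between participants. If baseline is gated, the largest distortion falls on Week 24 when there is no true change. All sizes rest on assumed FPG distributions; the documents supply none. The matter should be corrected, but it does not threaten the primary safety endpoint.

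**What to change.** **Protocol.** Remove footnote 6 from FPG and fasting insulin, so that both are drawn at the first fasting attempt of Weeks 12 and 48 whatever happens to the MMTT. The gate itself need not change.

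**SAP.** Define FPG and HOMA-IR at every visit, including baseline, as the first fasting sample in the visit window. Use re-booked pre-meal samples only for endpoints 6a-6c. Baseline must be covered: un-gating follow-up alone against a gated baseline would leave the +0.8 to +7.3 mg/dL shown above for Week 24.

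**If first samples were not kept.** Flag re-booked visits, baseline included, and report a sensitivity analysis without them. That analysis keeps only tests that passed the gate first time, plus plain draws, so it shows how much the results depend on re-booking but does not remove the bias.

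**Cost.** One extra glucose and insulin tube at re-booked visits, where HbA1c, CBC and the metabolic panel are already scheduled. SAP Section 3 reports enrolment in the past tense, with 3, 7 and 10 patients. If collection is finished, the cost is SAP wording and a flag.
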